9.7 Supply, transportation, receipt and storage conditions

GRASPA bag is shipped to Investigator's site in a qualified box allowing keeping medicinal product at controlled temperature $+2^{\circ}$ C to $+8^{\circ}$ C. The temperature evolution during shipment is continuously monitored by a recording sensor inside the pack.

Details regarding GRASPA reception should be documented by the recipient on the document "GRASPA Shipment and administration Form" (Appendix 6):

- Patient information consistency
- The integrity of the bag of GRASPA (absence of visual leak),
- The temperature indicator attached to the bag must show no sign that the product underwent out of range temperature. Otherwise, the investigator must contact ERYTECH Pharma for further instructions.
- The expiry date is compatible with the date and time of administration
- Presence of control card and Infusion double line (allowing the rinsing)

Presence of a Packaging for bag return

GRASPA should be managed and administered by the physician-investigator's department as soon as possible upon receipt and within the expiry time stated on the label.

The current shelf life of the product is 72 h from end of manufacture when stored between +2 °C to +8 °C (See the mention on the label).

GRASPA can be kept at room temperature up to a maximum of 6 hours before the injection (including the injection time). The product remains stable as showed in the stability studies. Do not freeze.

Instruction for receipt and administration of GRASPA are detailed in Appendix 6. Any issue happen, please contact ERYTECH Pharma for immediate appropriate recommendation.

9.8 Administration

Before administration of GRASPA, the following controls must be performed and should be recorded on the document "GRASPA Shipment and administration Form" (Appendix 6):

- The general appearance of the bag. The statements on the label are adapted according to the clinical trial.
- The product for color; dark red color should be observed. If it provides evidence that the product underwent excessive or low temperatures during shipment, the investigator must contact ERYTECH Pharma for further instructions. He/she will then determine whether to urgently request a new preparation.
- Presence of the document "GRASPA Shipment and Administration Form".

Consistency of information on "GRASPA Shipment and Administration Form" and the patient: name, forename, date of birth.

• An ultimate cross match blood test to check compatibility. Expiry date is compatible with date and time of administration.

If there is any doubt, the product must not be administered.

A compatibility test (cross-match) test between the patient's blood and GRASPA (removable segment tubes) should be performed in your local laboratory and GRASPA must not be administered in case of discrepancy.

GRASPA should not be administered beyond the maximum shelf life stated on the label.

GRASPA should not be transferred to another container before injection. Since no data regarding incompatibility are available, GRASPA should not be mixed or administered simultaneously with any other product, solution or medicinal product.

The administration should take place within the expiry time stated on the label of GRASPA.

GRASPA is administered by intravenous route using line devices provided with the product, under medical responsibility. If a pump is used, only devices specifically approved for blood transfusion should be used.

The rate of transfusion depends on the patient's clinical conditions. The mean duration for administration is about 45 minutes, longer in case cardiac impairment and must be adapted regarding the volume of the bag and patient's clinical conditions.

The entire content of the bag must be administered. The patient must remain awake and should be constantly monitored during the injection for occurrence of any adverse reactions and should be kept under observation for at least one hour post administration. In case of occurrence of a major symptom (e.g. malaise), GRASPA injection should be stopped immediately and the principal investigator must be informed.

At the end of the injection, the lines should be rinsed with 20-40 ml of physiological saline solution (0.9% NaCl).

The responsible person in charge of administration should record on "GRASPA Shipment and administration Form" (Appendix 6) information below:

- date and the time of injection
- name of the responsible person in charge of latest verifications before injection
- Whether the entire content was injected and the lines accurately rinsed, with full explanation if it was not the case.

Then this document should be faxed immediately to ERYTECH Pharma to confirm GRASPA administration.

N° [contact]

9.9 Traceability documentation on site

Traceability of reception controls and administration of GRASPA is documented with the document "Shipment and administration Form" (Appendix 6).

This document should be archived in the patient medical file.

This document could be duplicated as needed and forwarded to the responsible persons concerned.

The investigator is responsible for GRASPA accountability at the trial site.

9.10 Return of empty package and accountability

Empty bags must be returned to ERYTECH Pharma after GRASPA injection, using the material supplied to this attention. The bags will be checked for accountability and weighing at ERYTECH Pharma.

9.11 Case of non-administration of GRASPA

In case a bag of GRASPA is not administered to the patient, this event will be documented accordingly, providing full explanations for such case. Such case will be reported to EFS Lyon Rhône Alpes as well. These unused bags of GRASPA will be destroyed on site (biohazardous waste) or sent back to ERYTECH Pharma the same way as empty bags.

In case of any issue, resulting in the quality of the product being compromised, the product must not be administered. Investigator should contact ERYTECH Pharma who will organize product return. Investigator will assess the delay in case of a new production need to be sent, and if it is not acceptable he will decide the best treatment for her/his patient.

9.12 End of study treatment

Refer to section 8.11 for details

10. Concomitant medication

10.1 Cytarabine chemotherapy

All patients enrolled are to be treated with low-dose cytarabine as 40 mg daily (either one single dose of 40 mg or 20 mg twice daily according to local practice) subcutaneously for 10 days per course, each course occurring every 28 days (+/- 3 days).

The dosage could be adjusted to 20 mg once daily in case of toxicities at investigator's decision. Also, increased dose is acceptable if required by patient's status, as per investigator judgement.

10.2 Concomitant treatments during study

Concomitant medications requiring precautions:

- Oral Anticoagulants: fluctuations of coagulation factors and risk of thrombosis should be monitored with repeated measurements of INR
- Erythropoiesis stimulating agents except if deemed necessary by the investigator
- Growth Cell Stimulating Factors, except in case of severe infection at investigator's decision

Prohibited concomitant medications:

- Other antineoplastic agents
- Other L-asparaginase marketed products
- Other investigational product

10.3 Interactions

10.3.1 Contraindication:

A single GRASPA administration may lead to anti-L-asparaginase antibody production. These can trigger allergic reactions (mild reaction to anaphylactic shock) when another injection of L-asparaginase (whatever the form) administration is given. It is fully contra indicated to administrate any form of E. Coli L-asparaginase without a prior antibody test.

Yellow fever Vaccination: risk of fatal systemic vaccine disease.

10.3.2 To be avoided:

Vaccination with live vaccines: increase risk of serious infection especially in immunodeficient patients. Inactivated vaccines are preferred when available.

11.Safety

11.1 Adverse Events (AE)

11.1.1 Definitions

Adverse Event (AE): Any untoward medical occurrence in a patient or clinical investigation subject administered a medicinal product and which does not necessarily have a causal relationship with this treatment. An adverse event can therefore be any unfavorable and unintended sign (including an abnormal laboratory finding), symptom, or disease temporally associated with the use of a medicinal (investigational) product, whether or not considered related to the medicinal (investigational) product.

Any worsening, in frequency or severity, pre-existing condition should also be considered as an adverse event when occurring in patient administered a medicinal product.

Adverse Drug Reaction: Any noxious and unintended response to a medicinal product related to any dose administered. The phrase response to a medicinal product means that a causal relationship between a medicinal product and an adverse event is at least a reasonable possibility, i.e. the relationship cannot be ruled out.

Unexpected Adverse Drug Reaction: An adverse reaction, the nature, or severity of which is not consistent with the applicable product information (e.g. Investigator's Brochure for an unapproved investigational product or package insert/summary of product characteristics for an approved product).

11.1.2 Collection, recording and reporting of AE

11.1.2.1 Collection of Adverse Events

The following AE will be taken into account for this trial (grading reference used is the NCI-CTCAE version 4.0):

Any event will be recorded, irrespectively of the relationship with GRASPA / low dose cytarabine according investigator's opinion AND the grade. Similarly, any reaction linked to red blood cells (see section 11.3) during GRASPA administration will be recorded as an AE in the CRF.

Laboratory tests abnormalities

Any abnormal laboratory value should be reported as an AE.

- EXCEPTION: When ALL the following criteria, the investigator may decide not to be reported such the abnormal value:
 - The abnormal parameter IS part of the schedule of assessment AND
 - Is NOT associated with clinical symptoms AND
 - Is considered NOT medically significant by the Investigator, AND
 - Does NOT result in change of GRASPA / Low-dose cytarabine or other concomitant treatment administration

Disease Progression

In this study, the signs and symptoms corresponding to the disease progression or worsening (AML) **should not be recorded as AEs**. Death related to disease progression should not be reported as SAE.

The following should not be recorded as AEs, if recorded at screening:

- Pre-planned procedure, unless the condition for which the procedure was planned has worsened from the first trial related activity after the subject has signed the informed consent.
- Pre-existing stable conditions found as a result of screening procedures. Worsening of preexisting conditions must be reported.

If seriousness criterion is met, a SAE should be declared to ERYTECH Pharma drug safety, completing SAE report form (see section 11.2 and Appendix 7).

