Resistant disease (RD)	BM blasts increase of at least 5% vs nadir AND/OR PBBC increase of at least 15% in absolute count vs nadir OR at least 50% in percentage vs nadir – repeated at min 7 days interval
Relapse¶	Bone marrow blasts \geq 5%; or reappearance of blasts in the blood; or development of extramedullary disease
Stable disease	Failure to achieve at least Partial Remission AND no Resistant Disease criteria

Table 3: Response criteria in AML

* All criteria need to be fulfilled; marrow evaluation should be based on a count of 200 nucleated cells in an aspirate with spicules; if ambiguous, consider repeat exam after 5 to 7 days; flow cytometric evaluation may help to distinguish between persistent leukemia and regenerating normal marrow; a marrow biopsy should be performed in cases of dry tap, or if no spicules are obtained; no minimum duration of response required. ¶ In cases with low blast percentages (5-10%), a repeat marrow should be performed to confirm relapse. Appearance of new dysplastic changes should be closely monitored for emerging relapse. In a patient who has been recently treated, dysplasia or a transient increase in blasts may reflect a chemotherapy effect and recovery of hematopoiesis. Cytogenetics should be tested to distinguish true relapse from therapy-related MDS/AML. (adapted Döhner *et al* 2010, Diagnosis and management of acute myeloid leukemia in adults: recommendations from an international expert panel, on behalf of the European LeukemiaNet, Blood, 21 Jan 2010, vol 15, no 3; 453 - 474)

5. Benefit – risk analysis

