6.1 Type of trial

This is a multicenter, open label, randomized, controlled phase IIb trial.

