5.6.2.2. Progression-Free Survival (PFS)

PFS was originally defined as death due to progression in the protocol. However, to be consistent with regulatory guidance, which considers death from any cause in its definition, this endpoint was modified to be time elapsed between randomization and disease progression or death from any cause. Patients not known to have any of these events will be censored on the date they were last known to be event-free.

Progressive disease (PD) will be defined according to the section “AML-DISEASE EVALUATION” in the e-CRF as any of the following

- At least a 25% increase of BMBC compared with baseline (defined in the section “AML history / BM evaluation at baseline”, Bone Marrow Aspirate - Analyte - Blast)
- At least a 50% increase of PBBC compared with baseline
- Presence of extramedullary disease

Potential PD events presented by the patients will be reviewed and approved before database lock.

The methods for the analysis of PFS will be the same as those for OS. Specifically, PFS will be analyzed at the time of final analysis using a stratified log-rank test (stratified by PS) and displayed using Kaplan-Meier curves. Furthermore, a Cox model will also be used to test the effect of treatment and will include terms for prognostic factors (PS, age and karyotypic group).

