5.8.1. Adverse Events

Safety and tolerability will be assessed in terms of AEs, SAEs, laboratory data and vital signs, which will be collected for all subjects. The AE term (Investigator term) will be assigned to the lowest level term (LLT), and a preferred term (PT) will be classified by a high level term (HLT), a high level group term (HLGT) and a system organ class (SOC) according to the Medical Dictionary for Regulatory Activities (MedDRA) thesaurus, Version 15.1 or higher depending on the latest version available during the study. The intensity of AEs will be graded according to the NCI-CTCAE (version 4.0).

An overview of the number of patients with AEs and the corresponding number of AEs will be presented through tables and listings:

- Total AE count
- Any AE
- Any treatment-related AE (Cytarabine and/or GRASPA®)
- Any AE of CTCAE grade ≥ 3
- Any AE of CTCAE grade = 4
- Any treatment-related (Cytarabine and/or GRASPA®) AE of CTCAE grade ≥ 3
- Any severe treatment-related (Cytarabine and/or GRASPA®) AE
- Any AE with outcome of death
- Any serious AE

- Any treatment-related (Cytarabine and/or GRASPA®) serious AE
- Any AE leading to permanent discontinuation
- Any treatment-related (Cytarabine and/or GRASPA®) AE leading to permanent discontinuation (Action taken=Withdrawn)
- Any AE leading to temporary discontinuation
- Any treatment-related (Cytarabine and/or GRASPA®) AE leading to temporary discontinuation (Action taken=Reduced)

An AE will be considered as “treatment-related” if the relationship to study treatment is ticked “possible,” “probable” or “certain/definite”.

For subject counts, subjects are included only once, even if they experienced multiple events in that category.

All the following summaries will be displayed by treatment groups on the safety population:

- All AE by System Organ Class (SOC) term, Preferred Term (PT)
- AE Experienced by $\geq 5\%$ of Subjects by SOC term and PT
- Treatment-related (Cytarabine and/or GRASPA®) AE by SOC term and PT
- AE of CTCAE grade ≥ 3 by SOC term and PT
- AE of CTCAE grade = 4 by SOC term and PT
- Treatment-related (Cytarabine and/or GRASPA®) AE of CTCAE grade ≥ 3 by SOC term and PT
- Severe treatment-related (Cytarabine and/or GRASPA®) AE by SOC term and PT
- AE with outcome of death
- Serious AE
- Treatment-related (Cytarabine and/or GRASPA®) serious AE
- AE leading to permanent discontinuation
- AE leading to temporary discontinuation

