14.3.1.2.6	Incidence of Treatment Related Treatment Emergent Serious Adverse Events by Preferred Term	Safety
14.3.1.2.7	Incidence of Treatment Emergent Adverse Events of Special Interest by Preferred Term	Safety
14.3.1.2.8	Incidence of Treatment Emergent Adverse Events of Special Interest with Toxicity Grade of 3 or 4 by Preferred Term	Safety
14.3.1.2.9	Incidence of Treatment Emergent Adverse Events Occurring in at least 5% of Patients in either Treatment Group by MedDRA Preferred Term	Safety
14.3.1.3	Listing of Treatment Emergent Adverse Events Leading to Either GRASPA or Chemotherapy Withdrawal	Safety

Table/Figure Number	Output Title	Analysis Set
	Deaths	
14.3.2.1	Deaths and Deaths within 28 Days After Last IMP Administration	Safety
14.3.2.2	Listing of All Deaths	Safety
	Clinical Laboratory Data	
	Biochemistry	
14.3.3.1.1	Biochemistry – Summary of Shift From Baseline to Worst Post-Baseline Results	
14.3.3.1.2	Biochemistry – Summary Statistics for Clinically Significant Parameters by Treatment Group and Time	
	Hematology	
14.3.3.2.1	Hematology – Summary of Shift From Baseline to Worst Post-Baseline Results	Safety
14.3.3.2.2	Hematology – Summary Statistics for Clinically Significant Parameters by Treatment Group and Time	Safety
	Coagulation	
14.3.3.3.1	Coagulation – Summary of Shift From Baseline to Worst Post-Baseline Results	Safety

Table/Figure Number	Output Title	Analysis Set
14.3.3.3.2	Coagulation – Summary Statistics for Clinically Significant Parameters by Treatment Group and Time	Safety
	Other Safety Parameters	
	Vital Signs Data	
14.3.4.1.1	Vital Signs – Descriptive Statistics for Change From Baseline	Safety
14.3.4.1.2	Vital Signs – Listing of Clinically Significant Values	Safety
14.3.4.2	ECOG Performance Status – Shift From Baseline to Worst Post-Baseline Value	Safety

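### By-arm counts of fatal, serious and Grade 3 or higher AEs rest partly on open-label attribution to AML progression; splitting the planned death table by documented resistant disease or relapse would show how far this matters

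*Protocol*

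**What the plan says.** Protocol 11.1.2.1 takes two things out of safety reporting. Signs and symptoms that correspond to progression or worsening of AML are not recorded as AEs. For deaths the rule is "Death related to disease progression should not be reported as SAE". The section names no criterion, no confirming marrow or blood result, no timing and no adjudicator.

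The trial's disease criteria are in Protocol Table 3 (4.3.2), where progression is not a category. Resistant disease is defined by "BM blasts increase of at least 5% vs nadir" and/or a rise in peripheral blasts, with a repeat at 7 days or more. Relapse is marrow blasts of 5% or more, "or reappearance of blasts in the blood; or development of extramedullary disease".

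On masking, Protocol 6.1 states "This is a multicenter, open label, randomized, controlled phase IIb trial".

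SAP 5.8.1 plans by-arm summaries that include "Any AE with outcome of death", serious AEs and AEs of CTCAE Grade 3 or higher. SAP 8.1 plans table 14.3.2.1, "Deaths and Deaths within 28 Days After Last IMP Administration", and listing 14.3.2.2 of all deaths, both on the Safety population.

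**The concern.** An exclusion that depends on cause is only as objective as the judgement of cause. Here that judgement is made by someone who knows the arm, against a term the protocol's own criteria do not define.

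The protocol also shows why the judgement can be hard. Section 3.1 lists bleeding and infection risk among the features of AML. Sections 4.3.2 and 15.3.3 single out coagulation and hepatic events as harms to watch with GRASPA. Table 2 (3.4) reports hypofibrinogenemia in 26.9% and decreased antithrombin III in 11.5% of GRASPA patients in the earlier randomised ALL trial. A fatal bleed could in good faith be assigned either way.

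Safety of the combination is a stated objective, and the SAP Introduction says the trial is to inform a phase 3 decision. A by-arm difference in fatal or serious AEs, or the lack of one, could partly reflect different attribution in the two arms.

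**Working it through.** The plan gives no figure to reproduce. The documents do not state what share of deaths occur without progression, or how often such deaths are attributed to it, so no numerical size is offered. The check sets the rules side by side.

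**1. Does another rule bring an excluded event back?**
- 11.1.2.2 collects fatal and life-threatening SAEs throughout the study, but only events that are SAEs.
- 11.1.2.4 treats an unassessable event as possibly related, but only once it is a recorded AE or SAE.
- 11.1.2.5 makes any AE resulting in death an SAE, again only once it is an AE.
- 11.2.2 governs notification of SAEs.

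All four act after recording. None reverses an attribution to progression.

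**2. Is that attribution checked elsewhere?** SAP 5.6.2.2 says "Potential PD events presented by the patients will be reviewed and approved before database lock". That sentence serves PFS. It uses a baseline-referenced definition that differs from the nadir-referenced resistant disease of Table 3, and it is not linked to AE recording or cause of death.

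**3. Which outputs are exposed?** Let T be the deaths in an arm of size n that are not due to progression, and f the share of them called progression. Considering only this direction of error, the recorded fatal-AE proportion is T(1 − f)/n. The ratio of arm B to arm A is then the true ratio × (1 − f_B)/(1 − f_A). Equal shares lower both counts and leave the ratio alone. Unequal shares move it, up or down according to which arm has the larger f. The same reasoning applies to serious and Grade 3 or higher AEs whose symptoms overlap with AML.

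**4. Which outputs are not exposed?**
- Overall survival: death from any cause (Protocol 4.3.1).
- Table 14.3.2.1 and listing 14.3.2.2: all deaths, and deaths within 28 days of last study drug, with no attribution needed.
- Laboratory results: Protocol 8.7.1 schedules coagulation and hepatic tests on seven days of each course. SAP 5.8.2.1 summarises them by arm and identifies Grade 3 or 4 values.
- IDMC review: deaths reach the committee as overall frequencies and individual narratives (Protocol 11.6).

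**5. Is there a by-arm fatal-safety count that uses documented disease status?** None appears in the SAP text or the output titles in 8.1. Listing 16.2.6.3 shows PFS and survival variables per patient but is not a by-arm count. The table shells are in a separate document that was not available.

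**The case against.** Leaving progression events out of SAE reporting is a deliberate choice. The history of changes shows it entered at version 4, and AE reporting was revised again at version 6 at a regulator's request. It limits noise in a disease with high mortality. Protocol 11.1.2.1 otherwise asks for every event whatever its relationship or grade. Section 11.2.1 tells sites that death is the outcome of an event, so the underlying event should be named. A bleed in a patient with stable blasts is not plainly a symptom of progression. All of this stands, and it narrows the problem to a missing definition.

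Several stronger readings are tempting, and the documents do not support them:
- *Deaths by arm are unreliable.* They are not; all-cause and 28-day deaths need no attribution.
- *The fatal-AE count is the only measure of fatal toxicity.* The 28-day death count is another, and SAP 5.8.1 also plans fatal rows for pancreatic and diabetogenic events.
- *A toxic death called progression goes unreviewed.* It can miss the SAE stream, but the IDMC still receives a narrative.
- *The rule favours GRASPA.* Attribution could run either way, and nothing in the documents shows which.
- *The SAE rule must be rewritten.* That trade-off is debatable. Because resistant disease needs a repeat at 7 days or more, a rapid leukaemic death might never qualify and would become an SAE. The SAP postdates January 2017 and describes the end-of-recruitment IDMC review as done, so a protocol change would also come too late for many deaths.

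**Conclusion.** The concern holds in a limited form. The by-arm counts of AEs with a fatal outcome, serious AEs and Grade 3 or higher AEs depend partly on unmasked attribution to a term that Table 3 does not define, and no later rule corrects this. The direction and size are unknown. The primary endpoint and the attribution-free death and laboratory outputs are untouched. This is a cheap improvement to interpretation and does not threaten the main conclusion. It rests on the supplied SAP; if the separate table shells already split deaths by documented disease status, the point is met.

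**What to change.** Change the SAP before signature and database lock.

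1. Split table 14.3.2.1 by arm, for all deaths and for deaths within 28 days of last study drug, into deaths with and without resistant disease or relapse documented before death. Derive the flag by applying the protocol's Table 3 criteria to the AML assessment and blood-count data. Do not use the site's stated cause or the PD definition in SAP 5.6.2.2.
2. Beside the fatal-AE count in SAP 5.8.1, add a sensitivity row that also counts every death within 28 days of last study drug without documented resistant disease or relapse.

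The cost is one derived flag and one extra row. AML is assessed each course and blood counts are repeated within it (Protocol 8.6, 8.7.1), so no new data are needed.

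The downside is that some rapid leukaemic deaths without a confirmatory assessment will fall in the group without documentation, so the row should be labelled an upper bound. Its footnote should limit that label to deaths within 28 days in patients without documented resistant disease or relapse: treatment may continue after either (Protocol 8.11), and the row does not reach later deaths from toxicity in those patients. The all-deaths split will be less sharp after treatment ends, when visits are every 3 months.
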